8.4.3 Long Term Indication

Based on the results from the HM II Destination Therapy IDE study, it is assumed that 50% of the HM II Subjects will successfully achieve the composite primary endpoint. It is also assumed that the HM III will have a composite success rate of 55% due to less pump replacements at 24 months caused by thrombus or

driveline issues. It will take 174 HM III and 174 HM II Subjects (348 total Subjects) to achieve 80% power to prove the HM III is non-inferior to HM II when the margin of non-inferiority ($=\Delta$ in the above null and alternative hypotheses) is -10% using the Farrington-Manning risk difference approach to non-inferiority at a one-sided alpha = 0.025.

INTERMACS HM II data from 26 sites likely to participate in the HM III IDE study was reviewed. Eight hundred and twenty (820) patients were implanted with the HM II in 2012 at these sites and 52 (6%) received a transplant or explant due to myocardial recovery prior to 6 months. In order to have sufficient data to evaluate the 24 month success rate, an additional 9 Subjects will be randomized per arm (6% of 138) to account for these early outcomes. This results in a total of 183 Subjects randomized in each arm (366 total Subjects). It is assumed that 75 HM 3 patients will achieve 730 days of support on their original pump by the time the long-term cohort has completed the long-term follow up. This will provide sufficient data to evaluate the clinical reliability of the pump. If the HM 3 is proven to be non-inferior to the HM II for the long-term indication but 75 HM 3 pumps have not achieved 730 days of support, the submission of data to the Agency will be delayed until 75 pumps with durations of at least 730 days have been evaluated and included in the dataset.

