Study Hypothesis and Sample Size	
Short Term Indication Hypothesis:
 
 - HM3 non-inferior to HM II at 6 months - Assumes 87% composite success rate for HM3 and 85% for HM II at 6 months. - 294 Subjects provides 80% power to show non-inferiority when the margin of non-inferiority is 10% and alpha = 0.025. Sample size accounts for early transplants. 
Long Term Indication Hypothesis:
 
 - HM3 non-inferior to HM II at 24 months - Assumes 55% composite success at 24 months for the HM3 arm and 50% for the HM II arm - 366 Subjects provides 80% power to show non-inferiority when the margin of non-inferiority is 10% and alpha = 0.025. Sample size accounts for early transplants. 
Pre-Specified Secondary Analysis of Pump Replacements
 
 - When enrollment to evaluate the primary objective is complete, randomization will continue to enroll Subjects to determine if the pump replacement rate for HM3 is superior to HM II at 24 months - The pump replacement rate for the HM II is about 7% at 24 months in the United States. - In order to determine if the rate of HM3 pump replacements have been reduced to 3% at 24 months, 1028 Subjects will be required (power=0.8; alpha = 0.05, two-sided). This will require the randomization of 662 additional Subjects.
Study Duration	All randomized Subjects will be followed for 24 months or to outcome (transplant, explant, or death), whichever occurs first.

STUDY SYNOPSIS

Inclusion Criteria	
 1) Subject or legal representative has signed Informed Consent Form (ICF) 2) Age \geq 18 years 3) BSA \geq 1.2 m² 4) NYHA Class III with dyspnea upon mild physical activity, or NYHA Class IV 5) LVEF \leq 25% 6) a) Inotrope dependent OR b) CI $<$ 2.2 L/min/m², while not on inotropes and subjects must also meet one of the following: 
 • On Optimal Medical Management (OMM), based on current heart failure practice guidelines for at least 45 out of the last 60 days and are failing to respond • Advanced Heart Failure for at least 14 days AND dependent on intra-aortic balloon pump (IABP) for at least 7 days 7) Females of child bearing age must agree to use adequate contraception

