8.4.2 Short Term Indication

Based on a review of recent INTERMACS and Thoratec data, it is assumed that the HM II will achieve a composite success rate of 85% at 6 months. It is also assumed that the HM III will have a composite success rate of 87% due to less pump replacements at 6 months caused by thrombus or driveline issues. It will take 138 HM III and 138 HM II Subjects (276 total Subjects) to achieve 80% power to prove the HM III is non-inferior to HM II when the margin of non-inferiority is -10% ($=\Delta$ in the above null and alternative hypotheses) using the Farrington-Manning risk difference approach to non-inferiority at a one-sided alpha = 0.025.

INTERMACS HM II data from 26 sites likely to participate in the HM III IDE study was reviewed. Eight hundred and twenty (820) patients were implanted with the HM II in 2012 at these sites and 52 (6%) received a transplant or explant due to myocardial recovery prior to 6 months. In order to have sufficient data to evaluate the 6 month success rate, an additional 9 Subjects will be randomized per arm (6% of 138) to account for these early outcomes. This results in a total of 147 Subjects randomized in each arm (294 total Subjects).

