8.6 Analysis of Primary Endpoint

The HM III will be considered non-inferior to the HM II for both short and long term indications if the lower two-sided 95% confidence limit of the risk difference in the composite success between treatment arms (HM III minus HM II) is greater than -10% ("negative 10%", where 10% is the non-inferiority Δ in the above null and alternative hypotheses). Once non-inferiority is inferred, the data will be analyzed for superiority at a one-sided 0.025 level of significance using closed testing methods via the z-test of proportions using the normal approximation to the binomial distribution. Since the short term and long term evaluations are two distinct endpoints, no adjustment for multiple comparisons is required. The long-term evaluation will only be made if the HM 3 is non-inferior to the HM II for the short-term indication, thus no adjustment to alpha will be made.

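### The 80% in SAP 8.4.3 is the power of the 24-month test taken alone; under the SAP's short-term-first rule the long-term claim has about 71% power (73-74% with re-estimation)

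*SAP*

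**What the plan says.** SAP 8.4.3 sizes the 24-month endpoint as a single test. Its inputs are that "it is assumed that 50% of the HM II Subjects will successfully achieve the composite primary endpoint" and that "the HM III will have a composite success rate of 55" percent, with a 10-point margin, one-sided alpha of 0.025 and the Farrington-Manning method. It concludes: "It will take 174 HM III and 174 HM II Subjects (348 total Subjects) to achieve 80% power". Nine per arm are added for early outcomes, giving 183 per arm.

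SAP 8.4.2 treats the 6-month endpoint in the same way: "it is assumed that the HM II will achieve a composite success rate of 85% at 6 months", and "the HM III will have a composite success rate of 87" percent. This gives 138 per arm, raised to 147.

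SAP 8.6 then links the two: "The long-term evaluation will only be made if the HM 3 is non-inferior to the HM II for the short-term indication". It gives this as the reason for leaving alpha unadjusted. The SAP's summary of changes shows that version 2.0 added the sentence. The same version edited 8.4.3 to add the 75-pump condition and left the power statement as it was.

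The protocol synopsis states "366 Subjects provides 80% power to show non-inferiority when the margin of non-inferiority is 10% and alpha = 0.025", and protocol 13.5.3 reports the same sizing. Protocol 13.7 does not make the 24-month test depend on the 6-month result.

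**The concern.** Under the SAP's rule, success on the long-term claim means passing the 6-month test and then the 24-month test. A power figure for the second test alone is not the probability of obtaining that claim. The rule is used for its benefit (no alpha adjustment), but its cost in power is not reported. The 24-month result supports the long-term indication, so anyone taking 80% as the chance of that claim at the planned rates would underestimate the risk of missing it.

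**Working it through.** **Inputs.** 6 months: 0.87 v 0.85, 147 per arm (138 before inflation), SAP 8.4.2. 24 months: 0.55 v 0.50, 183 per arm (174 before inflation), SAP 8.4.3. The criterion in SAP 8.6 is a lower limit for "composite success between treatment arms (HM III minus HM II) is greater than -10" percent; one-sided alpha is 0.025.

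**1. Reproduce the plan's figures.** Farrington-Manning power with n per arm is

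Φ{[√n·(p_T − p_C + 0.10) − 1.96·s0] / s1},

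where s1² = p_T(1−p_T) + p_C(1−p_C), and s0² is the same expression at the maximum likelihood estimates restricted to a difference of −0.10.

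- 24 months: restricted estimates 0.474 and 0.574, s0 = 0.7027, s1 = 0.7053. For 80% power n = 172.6, so 173 per arm; the unpooled formula gives 174. Power is 80.3% at 174 and 82.2% at 183.
- 6 months: restricted estimates 0.794 and 0.894, s0 = 0.5082, s1 = 0.4905. For 80% power n = 137.9, so 138 per arm. Power is 80.0% at 138 and 82.5% at 147.

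The plan's 80% therefore reproduces, as stand-alone power.

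**2. Correlation of the two test statistics.** By the definitions in SAP 8.2, every failure before 6 months is also a failure before 24 months, so 24-month success implies 6-month success. Within an arm the covariance of the two indicators is p24(1 − p6).

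- Sum over arms: 0.55×0.13 + 0.50×0.15 = 0.1465.
- Variances: 0.87×0.13 + 0.85×0.15 = 0.2406, and 0.55×0.45 + 0.50×0.50 = 0.4975.
- With all patients shared: 0.1465/√(0.2406×0.4975) = 0.423.
- With the first 147 of 183 per arm shared: 0.423×√(147/183) = 0.38.

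**3. Probability that both tests succeed (bivariate normal).**

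| Per arm (6 / 24 months) | 6-month test alone | 24-month test alone | Both |
|---|---|---|---|
| 147 / 183 | 82.5% | 82.2% | 70.8% |
| 138 / 174 | 80.0% | 80.3% | 67.6% |

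Patient-level simulation at 147/183 (200,000 trials) gives 71.1% with Farrington-Manning tests and 72.0% with Wald tests. Both are shown because SAP 8.6 does not name the confidence-limit method.

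Sensitivity at 147/183: 67.9% for correlation 0, 70.8% for 0.38, 73.1% for 0.6. The ceiling of 82.2% is reached only with perfect correlation.

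**4. With the planned re-estimation.** The SAP 8.6.3 rule was simulated: interim at 74 per arm, conditional power formula, 50-80% zone, M′ equation, cap of 369 per group, and the increase X added to both endpoints. In 40,000 trials the sample size rose in about 16%. Both tests succeeded in 73.4% (Farrington-Manning final tests) or 74.1% (Wald). Simulation error is about 0.2 points.

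**5. Like-for-like gap.** At 147/183: 82.2 − 70.8 = 11.4 points. At 138/174: 80.3 − 67.6 = 12.7 points.

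**The case against.** The strongest reply is that nothing in SAP 8.4.3 is miscalculated. It names a test, an alpha, a margin, two rates and a sample size, and the power follows. Quoting power endpoint by endpoint is a normal way to size a fixed sequence, and the SAP nowhere presents 80% as the overall chance of the long-term indication. Once the 6-month test has been passed, the 24-month test succeeds with probability of about 70.8/82.5 = 86%. All of this stands, and a reader who infers an arithmetic error is mistaken. What remains is that the SAP fixes a procedure and gives no figure for what the procedure delivers on its second claim.

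A reader might also infer that the protocol's 80% is wrong as it stands. The documents do not support that: protocol 13.7 has no short-term-first rule, and without it the stand-alone figure (82% at 183 per arm) is the right one.

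A third inference would be that the trial is too small. Power of 80% for both tests together would take about 31 more per arm on each endpoint (178 and 214), but neither document sets such a target.

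Setting the printed 80% directly against 71-74% would suggest a gap of 6 to 9 points. That mixes sample sizes, because 80% belongs to 174 per arm and the other figures start from 147 and 183.

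Finally, the documents state no correlation. It need not be guessed, however: the nested definitions and planned rates give at most 0.42 with complete overlap, so the 82% ceiling is out of reach under the plan's own assumptions.

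**Conclusion.** The point holds as one of labelling and disclosure in the SAP. The 80% is the stand-alone power of the 24-month test. Under SAP 8.6, the probability of obtaining the long-term claim at the planned rates is about 71%, or about 73-74% with re-estimation. The chance of missing it is therefore about 29%, or 26-27% with re-estimation, against about 18% for the 24-month test alone at 183 per arm.

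This rests on the SAP's own rates, on 147 and 183 randomized per arm, on the short-term cohort being the first 147 per arm, and on a correlation of about 0.38 from the nested endpoints (68-73% for correlations of 0 to 0.6). It also depends on the short-term-first rule being kept when the SAP and protocol are reconciled. Type I error is not affected.

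**What to change.** In SAP 8.4.3, label 80% (174 per arm) and 82% (183 per arm) as the power of the 24-month test taken alone. Add that under the rule in 8.6 the power for the long-term claim is about 71%, or about 73-74% with the re-estimation in 8.6.3. State the assumptions beside it: the short-term cohort is the first 147 per arm, and the test statistics correlate at about 0.38, with 68-73% as the range for correlations of 0 to 0.6.

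Make the same change in protocol 13.5.3 and the synopsis only if the protocol adopts the short-term-first rule. If the rule is dropped instead, the stand-alone figure stands in both documents.

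The cost is a few sentences and a less favourable figure. Enrolment, alpha and tests stay as they are.

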8.5 Early Safety Assessment

The HM III IDE study will include an early safety assessment in lieu of a feasibility study. The first 10 HM III Subjects enrolled in the study will be included and their data analyzed when they have achieved 30 days of support. A table describing the 30 days status of the Subjects will be prepared. Adverse events will be presented as the percentage of Subjects who experience the event, the number of events and the event rate per 30 days. The data will be presented to the DSMB and FDA for a recommendation to continue the study and to expand to remaining study centers. All Subjects included in the early safety assessment will continue to be followed per protocol and will be included in the final Short Term and Long Term analysis.

8.6 Analysis of Primary Endpoint

The HM III will be considered non-inferior to the HM II for both short and long term indications if the lower two-sided 95% confidence limit of the risk difference in the composite success between treatment arms (HM III minus HM II) is greater than -10% ("negative 10%", where 10% is the non-inferiority Δ in the above null and alternative hypotheses). Once non-inferiority is inferred, the data will be analyzed for superiority at a one-sided 0.025 level of significance using closed testing methods via the z-test of proportions using the normal approximation to the binomial distribution. Since the short term and long term evaluations are two distinct endpoints, no adjustment for multiple comparisons is required. The long-term evaluation will only be made if the HM 3 is non-inferior to the HM II for the short-term indication, thus no adjustment to alpha will be made.

8.6.1 Primary Endpoint Stratified by Components of the Composite Endpoint

Differences in success rates between HM III and HM II will be performed for each component of the composite endpoint to evaluate if a single component is influencing the outcome. Specifically, for each component, two-sided 95%

confidence intervals of the differences and a z-test of proportions will be generated using the normal approximation to the binomial distribution.

8.6.2 Effect of Site Bias on the Primary Endpoint

In order to determine if a few superior investigational sites are influencing the primary endpoint results, a comparison of results across sites will be performed. Specifically, for each of the short term and long term outcomes, the significance of the treatment-by-site interaction effect will be assessed using logistic regression with the main effects for treatment and site, and with a treatment-by-site interaction effect. The treatment-by-site interaction effect will be tested at the 0.15 level of significance. A non-significant interaction or an interaction that is significant but only quantitative and not qualitative in nature will support the pooling of Subjects across sites for the primary analyses. Given that a number of sites will contribute only small numbers of Subjects, we will pool sites with less than 5 Subjects for the analysis.

8.6.3 Unblinded Interim Efficacy Analysis (Adaptive Design)

After 74 of the planned 147 patients per treatment group required for the analysis on the short term primary outcome are treated and followed for 6 months, an interim unblinded analysis comparing treatments on the 6-month short term primary outcome will be carried out. The short term primary outcome is the binary composite endpoint of survival to elective transplant if transplant is prior to 6 months, survival to myocardial recovery prior if recovery is prior to 6 months, or survival for 6 months of LVAD support free of a debilitating stroke (modified Rankin Score > 3) and free of reoperation to replace the pump. There will be no provision to stop the study at interim stage for overwhelming effectiveness and hence no adjustment of the significance level for the final analysis. The first purpose of the interim analysis is to calculate the power for non-inferiority, conditioned on the difference between treatments with respect to short term outcome rates and on the non-inferiority margin of 10% (or 0.10). Specifically, at the interim analysis, the conditional power for rejecting the following null hypothesis in favor of the alternative (i.e. for obtaining a non-inferiority conclusion at the final analysis for the short-term outcome) will be calculated:

$$H_0: \pi_{\text{HM III}} \leq \pi_{\text{HM II}} - \Delta$$

$$H_A: \pi_{\text{HM III}} > \pi_{\text{HM II}} - \Delta$$

where $\pi_{\text{HM III}}$ and $\pi_{\text{HM II}}$ are the short term success rates of HM III and HM II, respectively, and where Δ is the non-inferiority margin and is fixed at 10% (or 0.10). The conditional power will be calculated under the assumption that the interim observed estimate of the treatment difference is the true treatment difference. It will be calculated using the following formula as discussed in Lan and Wittes (1988):

$$1 - \Phi\left[\frac{Z_{1-\alpha} - B_\tau / \tau}{\sqrt{1 - \tau}}\right]$$

where

- a. $Z_{1-\alpha}$ is the $(1-\alpha)*100\%$ percentile of the standard normal distribution (i.e., the critical value used to assess non-inferiority at the final analysis at overall one-sided significance level α); here, with one-sided $\alpha = 0.025$, $Z_{1-\alpha}$ is set to 1.96.

- b. τ is the information fraction (= proportion of patients in the first interim analysis = r/M where r is the number of patients per group in the interim analysis and M is the planned number of patients per group for the final analysis). Here, it is expected that $r=74$, $M=147$, and $\tau=0.503$.
- c. $B_\tau = Z_\tau \sqrt{\tau}$ where Z_τ = the Farrington-Manning non-inferiority test statistic calculated on the interim observed data; specifically

$$Z_\tau = \frac{\hat{p}_{HMIII} - \hat{p}_{HMII} - (-\Delta)}{\sqrt{\frac{\tilde{p}_{HMIII}(1-\tilde{p}_{HMIII})}{n_{HMIII}} + \frac{\tilde{p}_{HMII}(1-\tilde{p}_{HMII})}{n_{HMII}}}}$$

where

- i. \hat{p}_{HMIII} = the interim observed estimate of the true success rate (π_{HMIII}) for HM III (=number of HM III subjects with success divided by number of HM III subjects in the interim analysis).
- ii. \hat{p}_{HMII} is the similarly defined interim observed estimate of the true success rate (π_{HMII}) for HM II.
- iii. \tilde{p}_{HMIII} and \tilde{p}_{HMII} are the interim maximum likelihood estimates of π_{HMIII} and π_{HMII} calculated under the above null hypothesis, as shown in Farrington and Manning (1990).
- iv. n_{HMIII} and n_{HMII} are the sample sizes used for the interim analysis from HM III and HM II, respectively.
- v. Δ is the non-inferiority margin of 0.10.

- d. Φ is the cumulative distribution function of the standard normal distribution.

Following the “promising zone” algorithm in Chen, Demets, Lan (2004), if the conditional power is <50% or >80% at the interim stage, the study will continue as is (there will be no stoppage of the study for futility nor will there be a sample size increase). If the conditional power is between 50-80% (the promising zone), the sample size will be re-estimated to achieve conditional power of 80% for the 6-month short term endpoint. . The total revised sample size per group, M' required to achieve a conditional power of 80% to assess non-inferiority at the final analysis using a non-inferiority margin of 0.10 (or 10%) is found by solving the following equation for M' (this formula is from Wang et al (2002), but it can also be derived algebraically from the above Lan and Wittes (1988) formula for conditional power by setting the above conditional power formula to 0.80 and solving for M'):

$$Z_{0.20} \sqrt{1 - \frac{r}{M'}} + Z_\tau \sqrt{\frac{M'}{r}} - Z_{1-\alpha} = 0$$

where $Z_{0.20}$ is the 20th percentile of the standard normal distribution (= -0.84) and where all other variables in this equation are defined above. This formula assumes the interim observed effect size between treatments is the true effect size between treatments.

Note that the final sample size for the 6-month short-term outcome will NOT be decreased below the currently planned final sample size for the 6-month short-term outcome. According to Chen, Demets and Lan (2004), in order to maintain Type I error at the nominal level, the sample size will not be increased to beyond a percentage of the original sample size as determined by the bound R , where R satisfies:

$$\frac{\sqrt{1+R}(\sqrt{1+R}-1)}{\sqrt{(1+R)-t}} = \left(\frac{|Z_{0.20}|}{Z_{1-\alpha}} \right).$$

With $|Z_{0.20}| = 0.84$ and $Z_{1-\alpha} = 1.96$, it can be shown that $R = 1.513$, which means the sample size can increase up to 151.3% of the original planned sample size (up to 369 per group) without inflating Type I error.

Also, any sample size increase for the 6-month short term outcome will also be applied to the final sample size used to assess the long-term outcome (there will be no interim unblinded analysis on the long-term outcome). The following table displays the sample size scenarios for each of the long-term and short-term outcome under various situations:

Endpoint	Sample Size Per Group at Interim	Sample Size Per Group at Final Analysis	
		In the Event of No Sample Size Increase at Interim	In the Event of a Sample Size Increase of X at Interim
6-month Short Term	After 74 patients per group are treated and followed for 6 months	After 147 patients per group are treated and followed for 6 months	After 147 + X patients per group are treated and followed for 6 months
24-month Long Term	This endpoint will not be analyzed in the interim.	After 183 patients per group are treated and followed for 24 months.	After 183 + X patients per group are treated and followed for 24 months.

The analyses on sample size re-estimation will be carried out by the independent statistician (non-voting) and presented only to the DSMB by the independent biostatistician. The DSMB will inspect the results and inform the sponsor of their final decision, without necessarily stating the reason for the decision. E.g., the DSMB will inform the sponsor “Continue the study as is” without informing the sponsor as to whether the reason is because the conditional power is <50% or because the conditional power is >80%; if the DSMB recommends an increase in sample size, the DSMB will not give a reason for the increase or any details behind the recommendation until the study is complete.

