13.7.3 Unblinded Interim Efficacy Analysis (Adaptive Design)

After 50% of Subjects are treated and followed for 6 months, an interim unblinded analysis comparing treatments on the 6-month short term outcome will be carried out. There will be no provision to stop the study at interim stage for overwhelming effectiveness and hence no adjustment of the significance level for the final analysis. The first purpose of the interim analysis is to calculate the power for non-inferiority, conditioned on the interim short term outcome rates in each treatment and on the non-inferiority margin of 10%. If conditional power is <50% or >80%, the study will continue as is; if conditional power is between 50-80%, the sample size will be re-estimated to maintain conditional power of 80% for the 6-month short term endpoint, controlling Type I error following the method in Wang et al¹⁰. Any sample size increase will then be applied to the long term endpoint.

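### The SAP's cap on the sample-size increase (R = 1.513, 369 per group) does not solve its own equation; the printed inputs give R = 0.867, at most 274 per group

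*SAP*

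**What the plan says.** The interim look at the 6-month endpoint is planned at 74 of 147 per group (SAP 8.6.3), an information fraction of 0.503. Outside the promising zone nothing changes: "if the conditional power is <50% or >80% at the interim stage, the study will continue as is". Inside it, "the sample size will be re-estimated to achieve conditional power of 80% for the 6-month short term endpoint". Protocol 13.7.3 gives the same target: "the sample size will be re-estimated to maintain conditional power of 80% for the 6-month short term endpoint". The SAP obtains the revised size M' "by setting the above conditional power formula to 0.80" and solving for M', and defines the quantile as the "20th percentile of the standard normal distribution (= -0.84").

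The SAP then sets a ceiling to protect Type I error: "the sample size will not be increased to beyond a percentage of the original sample size" fixed by R, where

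√(1+R) × (√(1+R) − 1) / √((1+R) − t) = |Z0.20| / Z(1−α).

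With 0.84 and 1.96 it reports R = 1.513, "which means the sample size can increase up to 151.3% of the original planned sample size (up to 369 per group". The Summary of Changes at the end of the SAP repeats the equation, inputs and result. Any increase X in the short-term size is also added to the long-term cohort, as 183 + X per group.

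**The concern.** The SAP prints the equation, its inputs and its answer together, so the answer can be checked, and it fails. The figure is the prespecified maximum in an unblinded adaptive rule and is the SAP's stated reason that Type I error is maintained. The independent statistician and the DSMB have to work from this text.

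The sentence is also ambiguous. Read literally, 151.3% of the planned size is 222 per group; the bracketed figure is 369; the equation gives 274. Because X carries into the long-term cohort, a wrong ceiling there would also misstate the largest possible long-term sample.

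**Working it through.** **Inputs (all SAP 8.6.3).** |Z0.20| = 0.84; Z(1−α) = 1.96; r = 74; M = 147; τ = 0.503. The t in the bound equation is taken as this information fraction. Target conditional power (CP) is 80% and the zone is CP 50–80%.

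**1. The plan's own figure.** 147 × (1 + 1.513) = 369.4, printed as 369. So 369 does follow from R = 1.513, and the fault lies in R.

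**2. Put R = 1.513 into the equation.**
- √2.513 = 1.5852, so the numerator is 1.5852 × 0.5852 = 0.9278.
- The denominator is √(2.513 − 0.503) = √2.010 = 1.4177.
- Left side: 0.9278 / 1.4177 = 0.654.
- Right side: 0.84 / 1.96 = 0.429.

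The two sides do not agree.

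**3. Solve for R.** The root at t = 0.503 is R = 0.8668. Check with R = 0.867: √1.867 = 1.3664; 1.3664 × 0.3664 = 0.5006; √1.364 = 1.1679; 0.5006 / 1.1679 = 0.4286, as required. The cap is 147 × 1.8668 = 274.4 per group (274.40 with t = 74/147 unrounded).

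**4. Can another reading rescue 1.513?**
- t = 0.5 gives R = 0.868.
- The more exact quantile 0.8416 gives R = 0.869 (274.7 per group).
- t = 0 gives only R = 1.041 (300 per group), and larger t gives less.
- Replacing 0.84 by 1.2816, the 90% quantile, with t = 0.5 gives R = 1.5129 and 369.4 per group. This reproduces the printed value, but the origin is inferred; neither document states a 90% target.

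**5. What the re-estimation rule can produce.** The SAP's equation for M' is −0.84 √(1 − 74/M') + Z √(M'/74) − 1.96 = 0. At interim CP of 50%, Z = 1.96 × √(74/147) = 1.391.

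| Interim CP | M' per group |
|---|---|
| 50% | 274.4 |
| 55% | 248.6 |
| 60% | 225.5 |
| 70% | 184.5 |
| 80% | 146.8 (held at 147) |

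M' would reach 369 only at an interim CP of 36.2%, where the SAP makes no increase.

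**6. Type I error** (one-sided; normal approximation integrated over the interim statistic, r = 74, M = 147, critical value 1.96):

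| Rule | Type I error |
|---|---|
| Fixed design | 0.0250 |
| Stated rule, cap 274 | 0.0245 |
| Stated rule, cap 369 | 0.0245 |
| 369 per group for every result in the zone | 0.0232 |

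**7. Consequences for X.** The printed cap implies X up to 369 − 147 = 222 and a long-term maximum of 183 + 222 = 405 per group. The equation implies X up to 274 − 147 = 127 and 183 + 127 = 310. Both are below the 514 per arm in SAP 8.16.

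**The case against.** The best case for leaving this alone is that nothing turns on it. The zone and the 80% target already limit M' to 274.4, so no re-estimated size changes because 369 is printed. The SAP's substantive claim also survives: even 369 per group throughout the zone gives 0.0232, below 0.025. Both points stand. They limit the weight of the finding, but they do not make the derivation right.

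The match between the bound and M' at CP 50% is not independent evidence. Substituting Z = 1.96√t and M' = M(1+R) into the M' equation turns it algebraically into the R equation. That is correct. It shows that the printed form of the equation is coherent and that the corrected cap coincides with the lower edge of the zone; the case against 1.513 rests on steps 2 to 4.

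The SAP states no rounding convention, and 369.4 printed as 369 would fit ordinary rounding too. Rounding down is preferred here because the bound is worded as a limit not to be exceeded. For r = 74 both conventions give 274. They differ for some other interim sizes, for example 274.80 at r = 73.

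Finally, if the sponsor had intended a 90% target, 369 would be coherent: M' at CP 50% would be 369.1. Both documents say 80% throughout, so R is the figure to correct, subject to one confirmation.

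**Conclusion.** The concern holds. R = 1.513 does not solve the printed equation. The SAP's inputs give R = 0.867 and a cap of 274 per group, so the printed cap is 95 per group (369 − 274) too high. The phrase giving 151.3% of the planned size is wrong as well, because 369 is 251.3% of 147.

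This is an error in a prespecified limit that should be fixed, with little practical effect: the cap of 369 never binds under the stated rule, Type I error is not inflated, and total enrolment does not change. The conclusion assumes that t is the information fraction of about 0.503 and that the target is 80%, as both documents state. The Type I error figures assume the normal approximation and an interim at exactly 74 per group.

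**What to change.** In SAP 8.6.3 replace R = 1.513, 151.3% and 369 with text such as: R = 0.867; the sample size can increase by up to 86.7%, to at most 274 per group (bound rounded down, and recomputed from the equation if the interim r differs from 74). State the implied limits: X at most 127, and at most 310 per group for the long-term cohort. For other interim sizes the rounded-down cap is 276 at r = 70, 275 at r = 72, 274 at r = 73, 273 at r = 75 or 76, and 271 at r = 80.

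Ask the sponsor to confirm that 80% is the intended conditional-power target, since a 90% quantile reproduces the printed R. The documents do not say whether the interim has taken place; if it is still ahead, the confirmation should come before unblinding.

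The cost is a wording change and no patients. The only re-estimated size that could differ arises at an interim CP of 50.00–50.07%, where M' (274.0–274.4) would round up to 275 and is held at 274. At CP of exactly 50% that gives a conditional power of 79.9% instead of 80%.
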